5.8. Multiple Comparisons/Multiplicity

For comparisons of safety outcomes, 5%-level two-sided tests will be made. Some of these may be implicit comparisons based on the overlap of group-level confidence intervals (i.e. non-overlapping 95% CIs mean rejecting the null hypothesis of no difference between groups at the 0.05-level).

To compare primary immunogenicity outcomes (antigen-specific plasma IgG binding responses, as measured by log AUC over time) across all groups, 5%-level two-sided tests will be used. When differences are found, pairwise comparisons between vaccination groups will be made using the Bonferroni-Holm step-down procedure [1] and a 5% significance threshold for the adjusted p-values; if no difference is found across all groups, no pairwise comparisons will be made. Collapsed comparisons will be considered separately and will be made with 2.5%-level two-sided tests, even when no pairwise differences are observed.

Further exploratory comparisons for immunogenicity endpoints across all groups will be adjusted for multiplicity by a Bonferroni adjustment: multiplying p-values by the number of assays in the same set (e.g. across antigens for a given antibody test; see Section 3.2.2 for sets of assays). Then a similar process as above will be followed, with pairwise comparisons following a significant overall test and Bonferroni-Holm step-down procedure (with a 5% significance level) to account for the multiple pairwise tests.

These adjustments are intended to improve control of the type-I error across comparisons for the same outcome measure and time point (e.g. Geometric Mean Titers (GMTs) for gp120A244 plasma IgG binding at Day 14) rather than across outcome measures and/or time. This level of type-I error control will still allow for exploratory findings that would be assessed further in future studies.

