8. IMMUNOGENICITY EVALUATION

8.1. Primary Immunogenicity Analysis

The primary immunogenicity endpoint is the magnitude of plasma IgG (antigen-specific) responses as measured by the endpoint titer, the same variable assessed in RV306. GMTs will be calculated for each group at each visit and the per-participant peak across all visits, along with 95% CIs (exponentiating the CI limits for the log GMT based on the normal distribution). Hypothesis testing is planned for targeted time points; this will be performed in order to aid in interpretation by helping to determine immune responses for potential further examination in future studies. First, group GMTs will be compared across all vaccination groups via ANOVA (null hypothesis that all groups share the same GMT) at the 5%-level, and if that is found to be significant, pairwise comparisons via 2-sided t-tests and the Bonferroni-Holm step-down procedure will be made and a 1% significance threshold will be applied. The two collapsed comparisons will be via 2-sided t-tests of log-GMTs at the $\alpha=0.025$ -level. If the data appear especially non-normal, nonparametric testing will be considered instead.

The reverse cumulative distribution (RCD) of titers (with endpoint titer on the x-axis and the proportion of participants with at least that titer on the y-axis) at each visit will be shown by vaccination group, separately for each antigen.

Seroconversion or seropositivity post-vaccination will be defined based on criteria given by the performing lab, and the number and percent of participants in each group achieving seroconversion/seropositivity at each visit will be presented along with the associated exact 95% Clopper-Pearson CI. The same group comparisons will be performed, via exact binomial tests and the same handling of significance and multiplicity.

Immune response over time (durability) will be assessed by the positive incremental area under the curve (AUC) based on a graph with log endpoint titer on the y-axis and visit day on the x-axis. For comparability between participants with different numbers of samples (visits) available, these values will be scaled by the week of the last available sample. If no sample is available for visits other than the first and last, no explicit imputation will be done, and the AUC will be calculated based on available samples. Log AUC will be analyzed similarly to the visit-by-visit titers.

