8.2. Additional Immunogenicity Analyses

Further immunogenicity analyses (see Section 3.2.2 for planned sets of assays) will be considered exploratory for testing purposes (see Section 5.8 for how significance and multiplicity will be handled), but they will otherwise follow a similar process as the primary immunogenicity analysis. For assays that are not conducted via titer experiments, the analysis values will be handled as log GMTs are, after appropriate transformation of the data to be

approximately normal when necessary; instead of RCD curves, boxplots will show the assay values for each group, by visit.

The kinetics of log IgG titers over time will be assessed via generalized estimating equations (GEE) models, with the immune response appropriately-transformed to assume normally-distributed error terms and RV546 vaccine dosage, adjuvant, study day, and all 2- and 3-way interactions included as covariates. These covariates will be assessed for significance at the 1%-level, and any findings will be considered hypothesis-generating. An unstructured working covariance matrix will be preferred, but other choices may be necessary due to computational challenges or poor model fit. These details will be described in the final report. Similar models may be fit for other assays, and these would also be considered exploratory.

To assess the relationship between possible confounders and the appropriately-transformed titers at the primary endpoint time point, a linear regression model will be fit as well, adjusting for vaccination group, age, sex, RV306 vaccination group, and time between final RV306 vaccination and RV546 vaccination. Covariates will be assessed for significance at the 1%-level, and again findings will be considered hypothesis-generating. Similar models may be fit for other assays also.

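### SAP 5.8 and SAP 8.1 set different significance thresholds (5% and 1%) for the same pairwise tests of the primary IgG endpoint, and the SAP's power table uses an alpha that applies to neither these tests nor the collapsed ones

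*SAP*

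**What the plan says.** SAP 5.8 covers the primary immunogenicity outcomes, which it describes as "antigen-specific plasma IgG binding responses, as measured by log AUC over time". An overall 5% test across all groups comes first. If it is significant, "pairwise comparisons between vaccination groups will be made using the Bonferroni-Holm step-down procedure [1] and a 5% significance threshold for the adjusted p-values".

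SAP 8.1 covers the same endpoint as visit-by-visit titers. A 5% ANOVA across the five vaccination groups comes first. If it is significant, "pairwise comparisons via 2-sided t-tests and the Bonferroni-Holm step-down procedure will be made and a 1% significance threshold will be applied". The section then adds: "Log AUC will be analyzed similarly to the visit-by-visit titers".

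For exploratory assays, SAP 5.8 multiplies the overall p-value by the number of assays in the set and then uses the "Bonferroni-Holm step-down procedure (with a 5% significance level) to account for the multiple pairwise tests". SAP 8.2 sends those assays there: "see Section 5.8 for how significance and multiplicity will be handled".

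On the dose and ALFQ contrasts the two sections agree. SAP 5.8 says: "Collapsed comparisons will be considered separately and will be made with 2.5%-level two-sided tests". SAP 8.1 says: "The two collapsed comparisons will be via 2-sided t-tests of log-GMTs", also at 0.025. SAP Table 4 gives detectable differences at two-sided 0.05 for those contrasts, for individual pairs and for all active versus placebo. Protocol 12.2.4 planned unadjusted 0.05 and named all active versus placebo among its comparisons.

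**The concern.** Endpoint, gate and step-down procedure are the same in both sections; only the cut-off differs. An analyst following 5.8 and one following 8.1 can reach opposite conclusions from the same titers. SAP 8.1 says these tests help decide which responses to examine in later studies. If the choice stays open until p-values are seen, the pairwise analysis is not pre-specified.

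If 8.1's 1% applies to Holm-adjusted p-values, the primary endpoint also meets a stricter pairwise cut-off than the exploratory assays, and the SAP gives no reason for this.

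Two smaller points follow. Table 4's 80% power belongs to tests at an unadjusted 5%, which the SAP does not use for its collapsed or pairwise comparisons. And all active versus placebo is powered in Table 4 but has no test in SAP 8.1 and no place in shell Tables 31, 34 or 39.

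**Working it through.** **1. Do the sections govern the same tests?** SAP 5.8 names log AUC, but its example of what the adjustments cover is a Day 14 GMT. SAP 8.1 names GMTs but extends its procedure to log AUC. Shell Tables 30 and 33 have an adjusted p-value column with a Holm footnote and no threshold. With five groups there are 5 × 4 / 2 = 10 pairs per antigen and time point. If the smallest raw p is 0.003, its Holm-adjusted value is 10 × 0.003 = 0.03, which is significant at 5% and not at 1%.

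**2. Reproducing SAP Table 4.** Inputs: 16 per active group, 16 pooled placebo, 32 versus 32 collapsed, 64 active. Two-sample t-test power is P(T > t(1−α/2, df)), with T noncentral t, df = n1 + n2 − 2 and noncentrality d / √(1/n1 + 1/n2). Solving for d at α = 0.05:

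| Comparison | 80% / 85% / 90% computed | Table 4 |
|---|---|---|
| 64 v 16 | 0.793 / 0.848 / 0.917 | 0.79 / 0.85 / 0.92 |
| 32 v 32 | 0.711 / 0.761 / 0.823 | 0.71 / 0.76 / 0.82 |
| 16 v 16 | 1.024 / 1.095 / 1.185 | 1.02 / 1.09 / 1.18 |

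The table is right for its stated alpha.

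**3. The same calculation at the alphas the SAP uses.** The first Holm step of 10 tests at 0.05/10 = 0.005 (5% adjusted) or 0.01/10 = 0.001 (1% adjusted).

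| Test | α | 80% / 85% / 90% (SD) | Power at Table 4's 80% difference |
|---|---|---|---|
| Collapsed, 32 v 32 | 0.025 | 0.79 / 0.84 / 0.90 | 71% at 0.71 SD |
| Pair, 16 v 16, 5% adjusted | 0.005 | 1.38 / 1.46 / 1.55 | 46% at 1.02 SD |
| Pair, 16 v 16, 1% adjusted | 0.001 | 1.61 / 1.68 / 1.78 | 25% at 1.02 SD |

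The pairwise rows are approximate, because they ignore the ANOVA gate and the later, easier Holm steps. With both included, simulated power for one active-versus-placebo pair at 1.38 SD is 82% (5% adjusted) or 63% (1% adjusted).

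**4. How often the two thresholds disagree.** Simulation: 40,000 trials per point, five normal groups of 16, ANOVA gate at 5%, two-sample t-tests, Holm over 10 pairs, the same shift in all four active arms, 1% taken as applying to adjusted p-values.

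| Shift (SD) | 0 | 0.5 | 0.79 | 1.0 | 1.2 | 1.5 | 2.0 | 2.5 |
|---|---|---|---|---|---|---|---|---|
| At least one pair discordant | 2.5% | 14% | 38% | 54% | 60% | 43% | 10% | 4% |

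Under the global null, any pairwise claim occurs in 3.0% of trials (5% adjusted) or 0.8% (1% adjusted), per antigen and time point.

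**5. Adding a third collapsed test.** The three contrasts are orthogonal, so the chance of any false claim per antigen and time point is:

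- two tests at 2.5%: 1 − 0.975² = 4.9%
- a third at 2.5%: 1 − 0.975³ = 7.3%
- a third at 5%: 1 − 0.975² × 0.95 = 9.7%
- three at 0.0167: 1 − 0.9833³ = 4.9%

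Simulation gave 5.1%, 7.5%, 9.9% and 5.0%.

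**The case against.** The strongest reply concerns what 8.1's 1% applies to, since it does not say raw or adjusted p-values. Read as raw, 1% is looser than 5.8 at the first five Holm steps (0.005 to 0.0083), so the claim that the primary endpoint is held to a stricter standard would not follow. This stands as a caution on direction, but it does not remove the conflict: a raw 1% rule still disagrees with 5.8 on some pair in about 25% of trials at a 1.0 SD shift. The adjusted reading is the more natural one, because Holm is named in the same sentence. The contrast with exploratory assays also holds only at the pairwise step, since their overall test carries a Bonferroni penalty.

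The 60% figure counts disagreement on any of ten pairs. Averaged over pairs, disagreement at that shift is about 9.5% (23% for active-versus-placebo pairs). Other mean patterns give other figures, higher ones included. The table in step 4 is therefore illustrative.

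Table 4 states its alpha, is offered as an illustration and repeats protocol Table 8, and Groups 1 and 2 had already stopped randomizing. Restating it changes no enrolment decision. Protocol 12.1 lists only dose and ALFQ as collapsed comparisons and says placebo is there mainly for blinding, and the shells still test each active arm against placebo. These facts make both points minor. The omission relative to protocol 12.2.4 remains.

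Finally, the shells print raw and adjusted p-values, so a reader could apply either threshold. That limits the damage but does not say which result the report will call a difference.

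**Conclusion.** The concern holds. SAP 5.8 and 8.1 give different thresholds for the same ANOVA-gated pairwise tests, and nothing else in the SAP decides between them. Under the equal-shift assumption with 1% read as adjusted, the rules disagree on at least one pair in between 2.5% and 60% of trials, most often near 1.2 SD. The collapsed tests need 0.79 SD for 80% power, against 0.71 SD in Table 4. An individual pair needs about 1.38 SD (5% adjusted) or 1.61 SD (1% adjusted) at the first Holm step, against 1.02 SD.

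Neither adjusted rule inflates the type I error for a given antigen and time point; SAP 5.8 openly leaves outcomes and visits uncontrolled. The harm is to clarity and reproducibility of a secondary, interpretive analysis in an exploratory Phase I trial. It should be fixed, and the primary safety objective is not affected.

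**What to change.** Before unblinding:

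1. State one pairwise threshold in both SAP 5.8 and 8.1, and say that it applies to Holm-adjusted p-values. The 5% adjusted rule is already spelled out in 5.8; the choice is the sponsor's.
2. Restate Table 4 at the alphas in use: 0.79 / 0.84 / 0.90 SD for the collapsed tests at 2.5%, and about 1.38 / 1.46 / 1.55 SD for pairs if 5% adjusted is kept. Label the pairwise figures as first-Holm-step approximations that ignore the ANOVA gate and later steps.
3. Decide on all active versus placebo. Either remove its row from Table 4 and record why the SAP omits this protocol comparison, or add the test to 8.1 and the shells with a stated alpha. An even split of 0.0167 over three tests keeps the false-claim rate at 4.9%. It would change the detectable differences to 0.83 / 0.88 / 0.94 SD (32 v 32) and 0.92 / 0.98 / 1.05 SD (64 v 16).
4. Record the move away from the protocol's unadjusted 5% in SAP section 11 or, as protocol 12.7 allows, in an amendment or the clinical study report.

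The cost is one aligned sentence, a less favourable Table 4 and one decision, with no added participants. If the three-way split is chosen, power for the dose and ALFQ tests at 0.71 SD falls from 71% to 65%.

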Relative to vaccine antigens from other pathogens, there is a particularly rapid decline of immune responses to HIV gp120 envelope proteins. Modulation of the response to vaccines with immunostimulatory adjuvants is one very promising approach to improve durability. The Army Liposome Formulation (ALF) family of adjuvants are ALFA (ALF adsorbed to aluminum salt), ALFQ (ALF mixed with the saponin QS21; US patent pending) (Beck, 2015), and ALFQA (ALFQ adsorbed to aluminum salt). Both ALFA and ALFQ are potent adjuvants, non-pyrogenic, and nontoxic in rabbit pyrogenicity and toxicology studies. ALFQ is an alternative to the successful but proprietary adjuvants, AS01B (liposomes containing both MPLA and the saponin QS21). ALFQ is potent in preclinical studies and contains 4 times the amount of MPLA and twice the amount of QS21 when compared to AS01B. An ongoing NHP study comparing HIV gp120 A244 formulated with either ALFQ or with aluminum hydroxide fluid gel (AHFG) has shown that animals that received ALFQ as the adjuvant compared to animals that received AHFG mounted significantly higher binding antibody responses to A244, gp70V1V2 A244, and V2 peptide (unpublished data). The responses were significantly higher after each immunization, as well as in ADCC responses, quantified using gp120 coated target cells. Given that antibody functions such as ADCC may have contributed to protection by non-neutralizing antibodies in RV144 vaccine recipients, ALFQ may contribute to increasing protective vaccine efficacy. In addition, data generated regarding the ALFQ adjuvant in this trial will help contribute to the safety database supporting its use with experimental antigens targeted towards other pathogens, including SARS-CoV-2.

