7.1.2. Immunogenicity Study Endpoints

Vaccine-induced immune responses will be assessed in study participants as detailed in the SOE ([Table 3](#)).

Humoral responses will be assessed by HIV-specific binding antibody assays, HIV-specific neutralizing antibody assays, and non-neutralizing antibody function assays at Days 0, 14, 168, and 336. Humoral mucosal immune responses in the rectal, semen and cervico-vaginal compartments will be assessed using non-invasive sampling methods (sponge, menstrual disc, and masturbation) at the same time points. Cell-mediated immune responses will be assessed utilizing invasive sigmoid and lymph node biopsies that will be performed at Day 14. Results of immunology assessments through invasive collection methods in the mucosal compartment are exploratory and will be mostly descriptive as performed in a limited number of participants.

Measurement of CD4+ and CD8+ T-cell effector function will be evaluated through response by cytokines such as IFN- γ and IL2. The CD4+ function will be assessed by the lymphoproliferation responses as measured by the functional CFSE assay. Innate immunity (e.g., NK cells) will be assessed by quantifying ADCC and ADCP, determining NK cell phenotype using various flow cytometric panels, cytokine array assays to characterize the type of cytokines elicited by this vaccine regimen with or without adjuvants, by the assessment of gene expression by DNA microarray and related techniques, and other related assays. B-cell responses will be characterized in blood and in diverse anatomical compartments (provided by sigmoid biopsies and lymph nodes biopsies) in a subset of participants. Host gene transcription profile and signature to vaccine antigens will be assessed by RNA sequencing and related techniques.

Leukapheresis will be performed at Day 14 in a subset of willing participants for in-depth investigations of the T-cell responses.

In the context of unknown immune correlates of protection, additional assessments may be performed as new scientific technologies and assessment tools are made available.

For further details, see Section [10.1](#).

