10.2.1. Humoral Immune Responses

HIV-specific Binding Antibody ELISA Assays will be performed to detect serum or plasma IgG and IgA binding antibodies to HIV-1 gp120, in particular to the V1V2 loops. Capture antigens will include V1V2 sequences from both subtype AE and Subtype B HIV-1 Env (gp70V1V2 92TH023 and gp70V1V2 Case A2), and HIV-1 Env gp120 proteins matched to sequences in AIDSVAX® B/E without the gD tag and with an 11 amino acid N-terminal deletion, represented as gp120 A244gD- D11 and gp120 MNgD- D11. Durability of IgG response will be assessed for each participant by estimating the decline in \log_{10} IgG from peak to 6- and 12-months post vaccination.

Neutralizing Antibody Assays will be measured as a function of reductions in luciferase (Luc) reporter gene expression after a single round of infection in TZM-bl cells using high throughput analysis. Stocks of molecularly cloned envelope-pseudotyped viruses have been prepared by transfection in 293T/17 cells (American Type Culture Collection) and titrated in TZM-bl cells. This assay has been formally optimized and validated and was performed in compliance with Good Clinical Laboratory Practices, including participation in a formal proficiency testing program. Tier 2 neutralization was assessed using a panel of 11 pseudoviruses, and a global panel.

Antibody Profiling will be conducted to assess antibody breadth and correlation of Fc receptor usage with antibody function. The current capacity for Antibody Profiling is the assessment of over 300 samples in one experiment. The beads presenting the HIV antigens will be distributed robotically in a high-throughput manner into 384 well plates. Similarly, the samples will be diluted robotically and incubated with the beads. Detection reagents will be added to the wells after washing. These detection reagents are inclusive of subclass, isotype and Fc receptor usage. Therefore, in one well, we will be able to capture 900 to 1000 data points from a single sample, and over 250,000 data points per experiment that will allow evaluation of the humoral immune response to these vaccine strategies.

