4.7. Immunogenicity Variables

Vaccine-induced immune responses will be assessed in study participants as detailed in the SOE. Humoral responses will be assessed by HIV-specific binding and neutralizing antibody assays at Days 0, 14, 168, and possibly at Day 336. HIV-specific binding antibody responses in the rectal, semen and cervico-vaginal mucosal compartments will be assessed using non-invasive sampling methods (sponge, cup, and masturbation) at Days 0, 14, and 168. Cell-mediated immune responses will be assessed via PBMCs and by utilizing optional invasive sigmoid and lymph node biopsies that will be performed at Day 14, dependent on sample availability. Results of immunology assessments through invasive collection methods in the mucosal compartments are exploratory and will be mostly descriptive as performed in a limited number of participants.

Measurement of CD4+ and CD8+ T-cell effector function will be evaluated through response by cytokines such as IFN- γ and IL2 at Days 0, 14, 168, and possibly at 336. The CD4+ function will also be assessed by the lymphoproliferation responses as measured by the functional CFSE assay at Days 0 and 14. Innate immunity (e.g., NK cells) will be assessed by quantifying ADCC, ADCP and cytokines produced by NK cells at Days 0, 14 and 168, determining innate cells' phenotype and function using various flow cytometric panels at Days 0, 1, 7, and 14, cytokine array assays to characterize the type of cytokines elicited by this vaccine regimen with or without adjuvants, and other related assays. Granulocytes and neutrophils (NET assay) will also be assessed in whole blood at Days 0, 14, and 168.

B-cell responses will be characterized in blood at Days 0, 7, 14, and 168 and in diverse anatomical compartments (provided by sigmoid and lymph nodes biopsies) in a subset of participants, dependent on sample availability.

Leukapheresis will be performed at Day 14 in a subset of willing participants for in-depth investigations of the T-cell responses.

In the context of unknown immune correlates of protection, additional assessments may be performed as new scientific technologies and assessment tools are made available.

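### The SAP's only labelled, formally tested durability measure is an AUC that mixes peak with persistence and depends on the last sample; the protocol's decline-from-peak measure is not carried over

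*SAP*

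**What the plan says.** **Protocol.** The Synopsis and 12.2.4 assess durability by the positive incremental AUC of log endpoint titer against visit day. Section 10.2.1 gives a second measure: "Durability of IgG response will be assessed for each participant by estimating the decline in" log10 IgG from peak to 6 and 12 months after vaccination. Section 7.1.2 schedules binding antibody assays together with "HIV-specific neutralizing antibody assays, and non-neutralizing antibody function assays at Days 0, 14, 168, and 336".

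**SAP.**
- 8.1 keeps the AUC as durability and adds a rule that the protocol does not contain: "For comparability between participants with different numbers of samples (visits) available, these values will be scaled by the week of the last available sample". On gaps it says: "If no sample is available for visits other than the first and last, no explicit imputation will be done"; the AUC is then computed from the samples that exist.
- 5.8 names log AUC over time as the primary immunogenicity outcome for group testing. The overall test is at 5% and the two collapsed comparisons (ALFQ, dose) are at 2.5%.
- 8.2 plans a GEE for log IgG kinetics with dose, adjuvant, study day and all interactions. It is tested at 1% and called hypothesis-generating. Table 35 takes Day 0 as the reference day.
- 4.7 says: "Humoral responses will be assessed by HIV-specific binding and neutralizing antibody assays at Days 0, 14, 168, and possibly at Day 336". Table 35 nevertheless has a Day 336 row.
- No SAP section or table shell carries the per-participant decline from peak.

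**The concern.** Protocol Section 5 presents adjuvants as a promising way to improve durability because "there is a particularly rapid decline of immune responses to HIV gp120 envelope proteins", and it reports RV306 durability as fold decline: 32-fold over 6 months without a late boost and 8-fold with one. A reader will therefore expect the ALFQ and dose comparisons to say something about the rate of decline. An AUC above baseline answers a different question, namely how much response there was over the period. A regimen with a higher peak and the same or faster decline can score higher and be reported as more durable.

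The scaling rule adds a second problem. It is meant to handle unequal sampling, but two participants with the same antibody curve receive different scores according to which samples exist.

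**Working it through.** **The plan's own figure.** SAP Table 4 gives a minimal detectable difference of 0.71 SD for mean log titer or mean AUC (32 vs 32, two-sided 0.05, 80% power). Noncentral-t power gives 0.711, so it reproduces. At the 0.025 level that the SAP uses for collapsed comparisons it is 0.787. This concerns precision and not what the AUC measures.

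**Inputs.** Binding visits are Days 0, 14, 168 and 336, or weeks 0, 2, 24 and 48 (schedule of evaluations). The 8-fold (0.90 log10) and 32-fold (1.51 log10) falls over 6 months are from Protocol Section 5. The SD of log titer is 0.5 to 1.0 (SAP 4.4.1), taken as log10 because the base is not stated. Rises, later falls and within-person correlation are assumptions.

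**Formula.** Score = trapezoidal area above the Day 0 value, in log10 × weeks, divided by the week of the last sample.

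**Step 1: one curve, different samples.** Rise +2.0 at Day 14, +1.1 at Day 168 (an 8-fold fall), +0.5 at Day 336.
- Segments: 2×(0+2.0)/2 = 2.0; 22×(2.0+1.1)/2 = 34.1; 24×(1.1+0.5)/2 = 19.2.

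| Samples available | Area / last week | Score | Versus complete |
|---|---|---|---|
| All | 55.3/48 | 1.15 | – |
| Ends Day 168 | 36.1/24 | 1.50 | +31% |
| Ends Day 14 | 2.0/2 | 1.00 | −13% |
| Day 14 missing | (24×1.1/2 + 19.2)/48 = 32.4/48 | 0.68 | −41% |

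**Step 2: weight of each visit with complete sampling.** Day 14: (24−0)/2 = 12, or 12/48 = 25%. Day 168: (48−2)/2 = 23, or 48%. Day 336: (48−24)/2 = 12, or 25%. In the Step 1 curve Day 14 supplies 12×2.0 = 24 of 55.3, or 43%.

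**Step 3: faster decline, higher score.**
- +3.0/+1.5/+0.9 falls about 32-fold by Day 168: (3.0 + 49.5 + 28.8)/48 = 81.3/48 = 1.69.
- +1.5/+1.4/+1.3 falls about 1.3-fold: (1.5 + 31.9 + 32.4)/48 = 65.8/48 = 1.37.

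**Step 4: behaviour of the tests.** Simulation with 32 per group, SD 0.5, correlation 0.5, baseline 2.0 log10, a further 0.3 log10 fall from Day 168 to Day 336, and 1,000 runs. The AUC is tested on the log scale at 2.5%. The Day 14-to-168 change is tested at 1%, the GEE's level.

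| Scenario | AUC rejects | Change rejects |
|---|---|---|
| Same 8-fold decline, rise 2.6 vs 2.0 | 100% | 0.9% |
| Same peak, 8-fold vs 32-fold | 95.5% | 97.8% |
| 32-fold with rise 1.85 vs 8-fold with rise 1.4 (areas equal) | 3.8% | 98.2% |
| Identical, half of one group ends Day 168 | 14.8% | 1.1% |
| Identical, all of one group ends Day 168 | 61.7% | 0.7% |
| Identical, 25% of both groups end Day 168 | 2.6% | 0.6% |

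In the third row a peak 10^(1.85−1.4) ≈ 2.8 times higher hides a 4-fold larger decline.

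**Step 5: what the GEE prints.** With three-way interactions and fractional dose as the reference, the adjuvant-by-day terms in Table 35 compare ALFQ with no ALFQ among fractional-dose recipients, each day against Day 0. The decline comparison is a difference of two such terms averaged over dose. The model can give it, but the SAP does not name it.

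**The case against.** Several points on the other side stand and limit the conclusion.

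- A reader might infer that the SAP replaced the protocol's measure with its own. It did not: the AUC is the protocol's measure in the Synopsis and 12.2.4. The SAP carried one of two protocol measures and added the scaling.
- A reader might infer that the plan cannot show decline at all. It can. The GEE contains the information, and SAP 8.1 gives GMTs at every visit and at peak, from which group fold changes can be read. What is missing is a per-participant decline and a stated contrast.
- A reader might call the AUC mostly peak height. Step 2 shows otherwise: Day 14 carries about a quarter of the weight, and the second row of Step 4 shows a clear response to decline when peaks are equal. In Step 3 the higher-scoring response is also still above the other at Day 168 (1.5 vs 1.4).
- A reader might take the ALFQ comparison to be biased by the scaling. That needs last-sample availability to differ between groups. Sequential enrollment, the optional interim immunogenicity analyses (SAP 5.6) and the uncertain Day 336 assay make it possible. No document says that it will occur, and none gives a dropout rate. If Day 336 is assayed for nobody, scaling is uniform among completers, but 12-month durability is lost.
- Decline alone has the opposite weakness. A flat non-responder, including a placebo recipient, shows no decline and would look most durable. Decline should therefore supplement the AUC.
- Safety is the primary objective of this Phase I trial, and SAP 8.1 presents immunogenicity testing as an aid to interpretation.

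None of this answers the missing decline measure, the failure of the scaling to deliver comparability, or the conflict over Day 336.

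**Conclusion.** The point holds in this limited form. The only durability measure that the SAP labels and formally tests combines peak height with persistence, so on its own it cannot separate a higher response from a slower decline. Under the stated assumptions it rejected in every run when only the peak differed, and in 3.8% of runs when a 2.8-fold higher peak masked a 4-fold larger decline.

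The scaling moves one assumed curve between 0.68 and 1.50 around a complete-data value of 1.15. With balanced early stopping the test keeps its level (2.6%). With one-sided early stopping it does not (14.8% to 61.7% at nominal 2.5%).

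The direction follows from the geometry. The sizes rest on the assumed rises, late falls and correlation, and on an SD at the low end of the plan's range; a larger SD would be expected to lower the rejection rates away from the null. The matter affects interpretation of a secondary objective and should be corrected before the immunogenicity analysis.

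**What to change.** 1. **SAP 8.1, decline.** Add the protocol's per-participant log10 decline from peak to Day 168 and to Day 336, compared among the active groups and in the two collapsed comparisons. Read it alongside the peak and the AUC, and describe the AUC as overall response over time.
2. **SAP 8.2, GEE.** Name the Day 168 minus Day 14 and Day 336 minus Day 14 contrasts for adjuvant and for dose, each averaged over the other factor.
3. **SAP 8.1, AUC.** Replace last-sample scaling with a common window: Day 0–168 for all, and Day 0–336 where Day 336 is available. Require the Day 14 sample, or show a sensitivity analysis without participants who lack it.
4. **SAP 4.7.** Reconcile the uncertain Day 336 assay with Protocol 7.1.2 and SAP Table 35, at least for plasma IgG binding.

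**What it buys.** For a Day 14-to-168 change, 32 vs 32, with 8-fold vs 32-fold decline (difference 0.602 log10) and SD of change = SD×√(2(1−ρ)), power at 2.5% is 96% to over 99% for SD 0.5, 66% to 97% for SD 0.75, and 40% to 79% for SD 1.0 (ρ assumed 0.3 to 0.7).

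**Cost.** SAP wording and one extra table. Day 336 binding uses stored plasma, so no extra blood is needed, though the assays must be run. Participants without Day 14 or the end-of-window sample drop out of the AUC; they are expected to be few, but the documents give no rate.
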